7.5.8 Healthcare Utilization (HCU)

HCU costs defined as an overall summary of costs related to prescription medications will be collected by the sponsor separate from the eCRF and are not covered by this SAP.

7.5.9 Percent of Subjects Taking Rescue / Use of Rescue Medication over Time

Subjects will be counted as having taken rescue on any particular day based on the rescue medication page of the eCRF and the at home rescue diary. If additional medications, other than the study rescue medications, appear on the concomitant medications page and can be identified as having been taken for bunion pain, those medications will also be counted.

The proportion of subjects taking rescue will be summarized for each study day through Day 15.

In addition, the proportion of subjects taking any rescue medication during the following periods: 0-96 hours, 24-48 hours, 24-72 hours, 24-96 hours, 96h to Week 1 and 96h to Week 2 and overall will be summarized and will be analyzed using Fisher's exact tests.

Separate summaries for opioid and non-opioid rescue use will be presented if sufficient data are present in the groups.

8 SAFETY EVALUATION

8.1 Overview of Safety Analysis Methods

All safety outcomes will be summarized using the safety population. Safety outcomes include:

- Incidence of treatment emergent adverse events (TEAEs) or treatment emergent serious adverse events (SAEs)
- Surgical site assessment/wound evaluations
- Physical examination (PE) of the lower extremities and vital signs, including neurosensory testing of both lower extremities
- Electrocardiogram (ECG) results
- Clinical laboratory test results

8.2 Adverse Events

Any untoward medical event that occurs after signing the informed consent form (ICF) is considered to be an adverse event (AE). All AEs will be recorded through 29 days (or 36 days as applicable) or ET, after the completion of surgery. SAEs will be recorded until 30 days after the 29 day follow up visit or ET, whichever occurs earlier. Treatment-emergent AEs are defined as AEs that start or worsen in severity after the end of study treatment infiltration (post T0). Verbatim terms used by investigators to identify AEs in the CRFs will be mapped to the appropriate preferred term (PT) and system organ class (SOC) using a standardized coding dictionary (MedDRA Version 21.0). All coding will be reviewed prior to database lock. All recorded AEs will be listed, but only TEAEs will be summarized.

For evaluation of causal relatedness to treatment, the categories are probably related, possibly related or unlikely related. For categorization in the summary tables, AEs designated as probably or possibly related will be considered to be related.

For the evaluation of event severity terms, the criteria are mild, moderate, severe or potentially life-threatening.

In addition to a listing of all TEAEs, treatment related TEAEs, serious TEAEs, Deaths, and TEAEs leading to premature discontinuation from the study will be provided.

An overall summary will be prepared giving for each treatment group and overall both the number of TEAEs, and the number of subjects with at least one TEAEs, as well as SAEs, treatment related TEAEs and TEAEs leading to premature discontinuation from study.

The number of subjects with AEs will be summarized for each treatment group by SOC and PT sorted in alphabetically by SOC, and then by PT within SOC. These summaries will be given by treatment in separate tables for each of the following TEAE event sets:

- All events
- Treatment related events
- Serious events
- Events leading to premature discontinuation from study
- Events by maximum severity

If a given subject experiences a TEAE that maps to the same PT/SOC more than once, the subject will be counted only once for the SOC/PT at the greatest severity (i.e., mild, moderate, or severe) and causality (i.e., attribution to study material).

Duration of a TEAE lasting more than 24 hours will be computed in days as the stop date of the event minus the start date plus 1 and will be reported in days. TEAEs lasting less than 24 hours will be computed as stop date/time minus start date/time. If reported as ongoing at the time of database lock, the stop date is defined as the date of the last visit or the last date of any event for the subject in the database, whichever is later. If a TEAE is considered resolved, but the stop date is missing, the last day of the month will be imputed if the month and year are available. If only the year is available, and the year is the same as the year of the last visit, the stop date will be the latest of the last visit date or latest event for the subject in the database. If the year of the event is prior to the year of the last treatment, the end day and month will be set to 31 December.

For missing or partial start and stop dates/times, the most conservative imputation will be used (AEs will be assumed to be temporally related to the study medication). [Table 8-1](#) will be used to impute any missing dates/times:

Table 8-1 Table of Imputation Rules for Missing AE Start Dates

Missing Date Portion	Prior to Treatment	Same as Treatment Start Date	After Treatment Start Date
Day	Month and Year < Month and Year of Study treatment:	Month and Year = Month and Year of Study treatment:	Month and Year > Month and Year of Study Treatment:
	Start Day = 1 Stop Day=last day of the month	Start Day = Day of first treatment Stop Day= last day of the month	Start Day = 1 Stop Day=last day of the month
Day and Month Define Day as above, then:	Year < Year of first treatment:	Year = Year of study treatment:	Year > Year of study treatment:
	Start Month = July Stop Month = Dec	Start Month = Month of study treatment Stop Month = Dec	Start Month = January Stop Month = Dec
Day, Month, and Year	To be conservative, completely missing start dates will be imputed using the date of study treatment, Missing end dates will be imputed using date of last study contact with the subject		
Time	Missing start times will be imputed as 00:01 Missing stop times will be imputed as 23:59		

After following these imputation rules, if the start date/time is imputed as a date after the end date/time, the start date/time will be set to the end date/time to provide a positive duration for the event incidence.

Missing assessments for AE study medication relationship or severity will be analyzed as related or severe respectively. No other imputation is planned for safety data.

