### 12.5.9. Assessment of Adverse Events

All SAEs will be documented and followed from the time the subject has signed the ICF until D29 or, if necessary, D36 after the completion of surgery. All SAEs and non-serious AEs will be documented and followed from the time of administration of study treatment until D29 or, if necessary, D36 after the completion of surgery. AEs that occur between Screening and the study procedure should be considered medical history and added to the subject's medical record. AEs that have been designated as possibly or probably related to study treatment will be followed until resolution or stabilization. Further details on AEs, including definitions, elicitation, and reporting are provided in [Section 13](#).

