#### **13.1.3.1. Serious Adverse Event Reporting**

Serious AEs must be reported to the Sponsor or designee within 24 hours of knowledge of the event. All SAEs that occur while a subject is receiving study treatment and within 14 days following the study completion visit (or 21 days following an ET if applicable) are reportable within 24 hours. During this follow-up period beyond study completion or after an ET, only

those SAEs considered to be possibly related to study treatment should be reported within 24 hours.

The procedure for reporting an SAE is as follows:

- All SAEs must be reported immediately (within 24 hours of discovery) by email to the CRO Medical Monitor or designee. Calls related to SAEs should first be directed to the CRO Medical Monitor or designee.

CRO Medical Monitor: [name], CPI

24/7 Emergency contact: [contact]

SAE Reporting email: [[contact]](mailto:[contact])

- The Sponsor's Medical Monitor is available for questions about safety-related issues: [name] JD MBA; [contact] or [[contact]](mailto:[contact]).
- The initial report should include all information known at the time of the report (additional information can be reported as discovered). Do not delay the initial reporting in order to obtain resolution or follow-up information.
- The site will enter into the electronic database (or fax, if the database cannot be accessed for any reason) an SAE report, or similar form, that includes the following information, as available:
  - Subject ID
  - Basic demographic information (age, gender, weight)
  - Outcomes attributed to the event (death, life-threatening hospitalization [new or prolonged], disability, congenital anomaly, required medical intervention to prevent permanent impairment/damage, etc.)
  - Onset date and severity of the event
  - Brief description of the event including frequency and severity of symptoms leading to diagnosis
  - List of relevant test results and laboratory data
  - Any other relevant history
  - Whether the study treatment was discontinued
  - Investigator's assessment of causality

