### **15.7.1. Adverse Events**

Adverse events will be coded by system organ class (SOC) and preferred term using the Medical Dictionary for Regulatory Activities (MedDRA) reporting system. Treatment-emergent AEs are defined as any of the following:

- Non-serious AEs with onset on the date of treatment with the study treatment through Day 29 or Early Termination, whichever occurs first;
- Serious AEs with onset on the date of treatment with the study treatment through 30 days after Day 29 or Early Termination, whichever occurs first;
- AEs that start before the start of treatment but increase in severity or relationship at the time of or following the start of treatment through Day 29 or Early Termination, whichever occurs first.

The number and percentage of subjects with TEAEs will be displayed for each treatment group by SOC and preferred term. Additionally, TEAEs will be tabulated for each treatment group by severity and by relationship to the study treatment. A listing of SAEs will be provided if applicable.

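### The protocol and SAP give three different end dates for SAE follow-up, so SAEs after Day 29 or Day 36 may be counted without being systematically collected

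*SAP*

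**What the plan says.** The current text contains three end points for SAEs.

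- **30 days after Day 29 or ET.** SAP 8.2: "SAEs will be recorded until 30 days after the 29 day follow up visit or ET, whichever occurs earlier". Protocol 15.7.1 gives the same period as part of its treatment-emergent definition: "Serious AEs with onset on the date of treatment with the study treatment through 30 days after Day 29 or Early Termination, whichever occurs first".
- **D29, or D36 if necessary.** Protocol 12.5.9: "All SAEs will be documented and followed from the time the subject has signed the ICF until D29", with D36 as the extension. Protocol 13.1.2 repeats this, with ±3 days around Day 29 where other sections give ±2. The synopsis safety endpoint also runs from T0 through D29.
- **14 days after completion, or 21 days after ET.** Protocol 13.1.3.1 says that all SAEs during treatment and "within 14 days following the study completion visit (or 21 days following an ET if applicable) are reportable within 24 hours". Protocol 13.1.3 uses the same 14 and 21 days as the limit for reporting hospitalizations as SAEs.

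The sentence in 13.1.3.1 that follows the 14/21-day rule says that, in the follow-up after completion or ET, only "those SAEs considered to be possibly related to study treatment should be reported" within 24 hours. The same section later requires every SAE to be entered on the AE CRF.

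For AEs in general, SAP 8.2 states: "All AEs will be recorded through 29 days (or 36 days as applicable) or ET, after the completion of surgery". Its definition of a treatment-emergent AE has a start (after T0) but no end date. SAP section 12 lists no change that reconciles these windows.

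**The concern.** Safety and tolerability is a secondary objective, and the SAP plans a summary of SAEs by treatment group (Table 14.3.1.4). Such a table is interpretable only if every subject was followed for SAEs over the period it claims to cover. Here the counting rule runs to 30 days after Day 29 or ET, while the protocol sections that tell sites what to document and report stop earlier, at two different points.

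An SAE on about Day 50 would count as treatment-emergent under Protocol 15.7.1. Nothing in Protocol 12.5.9, 13.1.2 or 13.1.3.1 would lead a site to look for it. Whether it reached the database would depend on spontaneous contact and on which section the site followed. Sites also cannot tell from 13.1.3.1 whether an unrelated SAE shortly after the completion visit needs a 24-hour report.

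**Working it through.** No sample-size formula applies. The check puts the windows on one day scale.

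**The plan's own figure.** The synopsis gives a maximum study duration of 83 days. Screening from D-45, plus D36, plus its 2-day window: 45 + 36 + 2 = 83. The figure reproduces. It also shows that the stated duration ends at the optional D36±2 visit and includes no later SAE follow-up.

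**Inputs.** Day 29 visit window ±2 days (D27 to D31); optional Day 36 visit ±2 days (latest D38); 30 days (Protocol 15.7.1, SAP 8.2); 14 days after completion or 21 after ET (Protocol 13.1.3, 13.1.3.1); D29 or D36 (Protocol 12.5.9, 13.1.2).

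**End of each window, by day of the completion visit**

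| Completion visit | Visit + 14 | Visit + 30 | Gap, 14-day text to 30-day text | Gap, D36 to 30-day text |
|---|---|---|---|---|
| D27 | D41 | D57 | 16 days | 21 days |
| D29 | D43 | D59 | 16 days | 23 days |
| D31 | D45 | D61 | 16 days | 25 days |

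**Days of the 30-day period not covered**

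- 14-day text, after completion: 30 − 14 = 16 days, or 16/30 = 53%.
- 21-day text, after ET: 30 − 21 = 9 days, or 9/30 = 30%.
- D29/D36 text: all 30 days if documentation stops at the Day 29 visit; nominally 59 − 36 = 23 days if it runs to D36.

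**Distance from the last scheduled contact.** The latest end of the 30-day window is D61 and the latest scheduled visit is D38: 61 − 38 = 23 days. Subjects who do not need the Day 36 visit have their last scheduled contact at Day 29.

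**If the 30-day window governed.** Maximum duration would be 45 + 31 + 30 = 106 days instead of 83.

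**The two 24-hour sentences in Protocol 13.1.3.1.** The first makes all SAEs in the 14/21-day period reportable within 24 hours. The second limits 24-hour reporting in that same period to possibly related SAEs. Both cannot be followed for an unrelated SAE. Both concern expedited reporting; neither limits entry on the CRF.

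**The case against.** The strongest reply is that this is a wording inconsistency with little effect. Several parts of it stand.

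- **SAP 8.2 is itself a recording statement.** A reader might infer that the counting window is longer than any collection window. The text does not support that: the SAP says SAEs are recorded for the same 30 days that Protocol 15.7.1 counts. The conflict is SAP 8.2 and Protocol 15.7.1 against Protocol 12.5.9, 13.1.2, 13.1.3 and 13.1.3.1.
- **The related-only limit is not a filter on the data.** A reader might infer that the first 14 days after completion would hold only related SAEs. The limit applies to 24-hour reporting. Section 13.1.3.1 still requires CRF entry of all SAEs. Section 13.1.3 keeps unrelated hospitalizations reportable for 14 days (21 after ET) and related ones without an end date.
- **The plan does not choose incomplete capture.** The gap arises if sites follow the shorter protocol text. It would not arise if the 30-day statement governed and were put into practice.
- **The effect may be small.** The percentages are shares of calendar days, not of events. Phase 1 had no SAEs in 37 subjects (29 active, 8 placebo). Protocol 15.7 plans no formal safety comparisons, and blinded arms under the same rules give no reason to expect bias between groups.

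The reply does not remove the conflict. In the protocol, which sites work from, the only 30-day SAE statement sits in the statistics section, and no visit or call is scheduled to put it into effect. CRF entry of all SAEs does not lengthen the period over which sites are told to document them.

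**Conclusion.** The concern holds as a conflict between stated rules. Protocol 15.7.1 and SAP 8.2 run to 30 days after Day 29 or ET; Protocol 12.5.9 and 13.1.2 stop at D29 or D36; Protocol 13.1.3 and 13.1.3.1 use 14 or 21 days. Section 13.1.3.1 also contradicts itself on 24-hour reporting.

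The size depends on which text sites follow. Under the 14/21-day text, the last 16 of 30 days after completion, or 9 of 30 after ET, are not systematically covered. Under the D29/D36 text the gap is 30 or 23 days. This assumes that sites work from the protocol's collection and reporting sections and that no contact beyond D36±2 is added elsewhere. The documents give no basis for a number of missed events.

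The consequence is limited to the completeness of late SAE counts. SAEs through D29 are covered by all of the texts for subjects who stay in the study, and the efficacy analyses are unaffected. The point should be corrected because the SAE table would otherwise claim a period that the protocol does not ensure is observed.

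**What to change.** 1. Choose one SAE end date, for completion and for ET, and state it identically in Protocol 12.5.9, 13.1.2, 13.1.3, 13.1.3.1 and 15.7.1 and in SAP 8.2. The choice is the sponsor's. Align the synopsis endpoint with it.
2. State that all SAEs up to that date are recorded regardless of relatedness.
3. Set the treatment-emergent SAE tabulation window equal to that recording window, and give the SAP's treatment-emergent definition an explicit end date. List SAEs reported later separately.
4. Reconcile the two 24-hour sentences in Protocol 13.1.3.1.
5. Clarify the closing condition on the 30-day period in SAP 8.2 and Protocol 15.7.1. It can mean 30 days after the earlier of the Day 29 visit and ET, or that recording stops at ET itself.

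**Cost.** Choosing D29/D36 or the 14/21-day period needs mainly text alignment. Choosing 30 days also needs a contact after D36±2, a stated maximum duration of about 106 days instead of 83, and possibly a few more reports of unrelated SAEs.

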- Record vital signs: 1, 2, 4, 6, 12, 24 and every 8 hours thereafter (if awake at time of assessment between the hours of 00:00 and 06:00) until discharge from the inpatient unit (may not miss two consecutive assessments). There will be a  $\pm 5$  minute window allowed for the collection of vital signs in the first 4 hours after the end of surgery, after which will be a  $\pm 15$  minute window allowed. Daily temps can be recorded along with vital signs per site SOPs at 1, 2, 4, 6, 12, 24, and every 8 h thereafter until discharge from the inpatient facility (if awake at the time of assessment between hours of midnight and 6 a.m.).
- Perform interim PE: surgical site assessment and neurosensory exam of the foot proximal to the surgical site with contralateral comparison prior to discharge from the inpatient unit.

- Perform ECG: at 24 ( $\pm$ 2) hours after surgery.
- Clinical laboratory tests (chemistry, hematology and urinalysis): at 96 hours prior to discharge from the inpatient unit.
- If the subject is participating in the PK study, obtain whole blood for PK analyses: at baseline (within the 30 min before the start of study treatment dosing), and T5min, T10 min, T15min, T30min, T45min, and T1, T1.5, T2, T2.5, T3, T4, T6, T8, T12, T16, and T24h, for a total of 17 samples).
- Subjects with inadequately controlled pain may request and receive rescue medication at any time; however, subjects will be encouraged to receive rescue only for an NRS  $\geq$  4. Additionally, subjects should be encouraged to wait at least 1 hour after completion of surgery (EOS) before utilizing pain rescue medication, if possible. NRS must be completed within 15 minutes prior to use of pain rescue medication if the time between rescue request and consumption is prolonged.
- Document the time to first use of rescue medication after T0 (between T0 and T24h) and after T24 (between T24h and T96h).
- Document concomitant medication use including doses and times taken
- All AEs that occur from the time a subject's informed consent but prior to study treatment will be captured in the medical history. All AEs and SAEs will be documented and followed from the time of administration of study treatment and will be considered treatment-emergent AEs (TEAEs).

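### SAP Table 8-1 imputes a missing start time as 00:01, so untimed adverse events on Day 0 fall before T0 and, unless they worsen, drop out of the TEAE summaries

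*SAP*

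**What the plan says.** SAP 8.2 (Adverse Events) ties the window to T0: "Treatment-emergent AEs are defined as AEs that start or worsen in severity after the end of study treatment infiltration (post T0"). SAP section 3 makes T0 the completion of study drug administration, which is a clock time on Day 0. SAP 8.2 also limits what is tabulated: "All recorded AEs will be listed, but only TEAEs will be summarized".

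For missing or partial dates and times, SAP 8.2 states its aim just before Table 8-1: "the most conservative imputation will be used (AEs will be assumed to be temporally related to the study medication"). The table then sets the rules, among them:

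- day missing, month and year equal to those of treatment: "Start Day = Day of first treatment"
- date wholly missing: "completely missing start dates will be imputed using the date of study treatment"
- time missing: "Missing start times will be imputed as 00:01"

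No row treats Day 0 differently. The text after the table handles missing relationship (taken as related) and missing severity (taken as severe), and plans no further imputation for safety data.

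The protocol's analysis section works by date. Protocol 15.7.1 includes "Non-serious AEs with onset on the date of treatment with the study treatment through Day 29 or Early Termination, whichever occurs first", with a parallel entry for serious AEs. Protocol 9.1.4 works from dosing: "All AEs and SAEs will be documented and followed from the time of administration of study treatment and will be considered treatment-emergent AEs (TEAEs"). The protocol synopsis (Safety Parameter Assessment Times; Safety Endpoints) uses post T0, as the SAP does.

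**The concern.** Imputing a missing time to the start of the day is conservative when the window opens by date, because the AE is then kept. It is the opposite when the window opens at a clock time later that day, because every untimed AE on that day falls outside. SAP 8.2 combines the early-time rule with the clock-time window. The date rows move doubtful AEs onto Day 0 so that they will count, and the time row then removes them.

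Safety and tolerability is a secondary objective, and the summary tables contain only TEAEs. Day 0 is the day of dosing, so an acute reaction to study treatment would be expected then. With 36 subjects per arm, one omitted subject turns a row of 1/36 (2.8%) into 0/36.

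There is a secondary point. Dosing has four steps (Protocol 9.1.2.2) and T0 is the end of the last, so there is a short interval in which drug is in the wound but T0 has not been reached. The protocol gives conflicting answers on whether an AE in that interval is treatment-emergent, and the SAP adopts one of them without comment.

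**Working it through.** The plan states no figure on this point, so the check applies the written rules to test records.

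**Inputs.** Window: start strictly after T0 (SAP 8.2). Imputation: Table 8-1. Comparison: onset on or after the treatment date (Protocol 15.7.1). The documents give no clock time for surgery, so T0 was assumed at 07:00, 08:00, 10:00, 12:00 and 15:00. Randomization on the day of surgery and the Mayo block both precede dosing, so T0 cannot plausibly be as early as 00:01. The imputed start lies between 6 h 59 min (T0 at 07:00) and 14 h 59 min (T0 at 15:00) before T0.

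| AE record | Start used | TEAE under SAP 8.2? | TEAE under Protocol 15.7.1? |
|---|---|---|---|
| Day 0, time missing | Day 0, 00:01 | No | Yes |
| Day and time missing, treatment month | Day 0, 00:01 | No | Yes |
| Date and time wholly missing | Day 0, 00:01 | No | Yes |
| Onset 5 min before T0, during dosing | as recorded | No | Yes |
| Control: Day 0, 1 h after T0 | as recorded | Yes | Yes |
| Control: Day 1, time missing | Day 1, 00:01 | Yes | Yes |

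The result was the same at all five values of T0. The two controls show that the fault is confined to Day 0. A record with both day and month missing in the treatment year also reaches Day 0, because Table 8-1 then takes the treatment month and applies the day rule. The one route back in is worsening in severity after T0.

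**Size.** The documents do not give the number affected, so this is an illustration. Protocol Table 2 (Phase 1, preliminary) has 22 TEAEs in 29 active subjects and 6 in 8 placebo subjects. Scaled to 108 active and 36 placebo: 22/29 × 108 = 81.9 and 6/8 × 36 = 27.0, total 108.9. The Day 0 share and the missing-time share are assumptions.

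| Assumed Day 0 share | Day 0 events | 5% without a time | 20% without a time |
|---|---|---|---|
| 20% | 21.8 | 1.1 | 4.4 |
| 50% | 54.5 | 2.7 | 10.9 |

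The 5% column is the more plausible. Protocol 15.5.5, SAP section 3 and SAP 8.2 all compute short AE durations from start and stop times, so times are expected, and Day 0 is spent under inpatient observation. The list of AE items in Protocol 13.1.2 names an onset date and no onset time, which leaves some doubt.

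**Dosing interval.** Of the 14 mL, 2 + 9 + 2 = 13 mL (13/14 = 93%) is given before the last step. For an AE in this interval the protocol says:

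- synopsis: post T0 only, so not a TEAE
- 9.1.4 and 12.5.9: AEs followed from administration, start or end not specified; 9.1.4 calls these TEAEs
- 15.7.1: by treatment date, so a TEAE

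SAP section 12 records no choice among these.

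**The case against.** The strongest reply is that the sentence above Table 8-1 states the governing intent. A programmer who follows it would count these AEs, so the fault would be ambiguity and not a wrong rule. The intent is indeed clear, but the table is the operative instruction. It names 00:01 without exception, and nothing gives the sentence priority over it. Applied as written, the rule produces the wrong class.

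The reply on size stands. Times are evidently meant to be collected, few should be missing in an inpatient unit, affected AEs remain in the listings, and Protocol 15.7 plans no formal safety comparisons.

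The reply on the dosing interval also largely stands. Post T0 is the synopsis's own definition, so the SAP did not invent it. What remains is a protocol conflict that the SAP leaves open.

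A reader might infer four stronger things that the documents do not support:

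- **That these AEs are lost from every TEAE table in all cases.** Those that worsen after T0 still count.
- **That a serious reaction during dosing would be missing from the SAE table.** SAP 8.2 lists serious events among its TEAE sets, but planned Table 14.3.1.4 is titled as a summary of SAEs, so the matter is not settled.
- **That nearly all Day 0 events would be lost because Protocol 13.1.2 lists no onset time.** The duration rules imply that times are recorded.
- **That losses during dosing are likely and fall on the CA-008 arms.** Protocol 7.1.4 does describe an immediate effect of capsaicin. However, dosing takes place under sedation after a bupivacaine block, when burning is unlikely to be reported, and a symptom first reported after T0 would count. The documents give no rate for such events.

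**Conclusion.** The point holds for imputation. As written, SAP 8.2 and Table 8-1 together class an untimed AE on Day 0, whether recorded there or dated there by imputation, as not treatment-emergent unless it later worsens. That contradicts the aim stated in the same section and the onset-date rule in Protocol 15.7.1. For any affected record the result does not depend on the hour of surgery.

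The effect is limited to descriptive safety summaries. The number affected cannot be derived from the documents. About 1 to 3 of roughly 109 events is a reasonable guess, and it rests on Phase 1 rates carrying over, a Day 0 share of 20% to 50%, and 5% of Day 0 times missing. The last two are assumptions without a source in the documents. The correction is worth making because the rule gives a wrong result and is cheap to repair.

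The dosing interval is secondary: an unresolved inconsistency in the protocol that the SAP should settle.

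**What to change.** In the time row of Table 8-1, add a Day 0 exception. When the start date is Day 0, recorded or imputed, and the time is missing, set the start to one minute after T0, or class the AE as treatment-emergent directly, unless a recorded fact shows onset before study treatment. A stop time before T0 would be such a fact. The existing rule that moves an imputed start back to the stop time already gives the right class there. A start set exactly to T0 would not be enough, because SAP 8.2 requires onset after T0.

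For the secondary point, state in SAP 8.2 how an AE between first instillation and T0 is classed. Opening the window at the start of administration is preferable. Record the choice, and its departure from the synopsis, in SAP section 12. If the time of first instillation is not on the CRF, the date rule of Protocol 15.7.1 does the job with no new data.

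The cost is one table cell, one sentence in SAP 8.2 and an entry in section 12, made before unblinding. The downside is that a few Day 0 events due to sedation or the block may be counted as TEAEs. Randomization should spread these evenly over the arms.
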